5.1 Overall design

This is a non-commercial, open label trial of a licensed drug designed to primarily provide preliminary efficacy and safety data for the use of Exenatide in MSA. This will be a simple parallel group design and include a 48-week exposure period. Detailed evaluations will take place at Screening, Baseline, 12, 24, 36, 48 and 96 weeks.

Patients will be randomly allocated into 2 groups to receive either:

- Exenatide extended release 2mg subcutaneous injection once weekly for 48 weeks together with standard treatment options, n~25,
or
- Standard treatment options, n~25

[figure not shown]
The control arm will attend all the same visits as the Exenatide group. Separate randomisation lists will be generated for patients with MSA-P or MSA-C.

The control group of patients are very important in view of the continued neurodegenerative process of MSA that leads to a mean 7.8 point decline in UMSARS scores per year (Poewe et al. 2015).

All participants will be invited for face to face visits at all timepoints. If a participant is unable or unwilling to attend any of the follow up assessments (12,24,36,48,96 weeks), they may be offered the option of a home visit by 1 or more members of the trial clinical team if staffing levels permit.

This trial will also assess the safety and tolerability of Exenatide when administered to patients with MSA. Encouraging results will be used as a basis for application for funding for a larger double blind placebo controlled RCT and will be used to inform upon sample size calculations for such a trial. This drug already has a license for the treatment of patients with Type II Diabetes and there is extensive safety data from phase 3 trials of its use in this patient group.

.

6 Investigational Medicinal Products and Non-Investigational Medicinal Products

6.1 Name and description of IMP(s)

Exenatide (extended-release for injectable suspension) - “Bydureon” 2mg subcutaneous once weekly injection or “Bydureon BCise” 2mg subcutaneous once weekly injection.

Exenatide is a licensed treatment indicated in adults 18 years and older with type 2 diabetes mellitus to improve glycaemic control in combination with other glucose-lowering medicinal products including basal insulin, when the therapy in use, together with diet and exercise, does not provide adequate glycaemic control. This study will investigate Exenatide in a novel indication in Multiple System Atrophy.

The Bydureon dual-chamber pen contains Exenatide powder and solvent in a Type 1 glass cartridge sealed at one end with a chlorobutyl rubber stopper and an aluminium seal, and at the other end with a chlorobutyl rubber piston. The two chambers are separated by a second chlorobutyl rubber piston. There is one needle supplied per pen. Each carton also contains one spare needle. Each pack contains 4 single-dose pre-filled pens and a multipack containing 12 (3 packs of 4) single-dose pre-filled pens.

From 31 March 2021, the Bydureon pen is being replaced by Astra Zeneca by a newer, easier to use device- the Bydureon BCise pen. The discontinuation of Bydureon is not due to quality or manufacturing issues and does not affect trial participants who are currently on Bydureon. The Bydureon BCise pen is a single chamber pen, with a needle already attached, containing the suspension and thus only needs shaking by the user to ensure the suspension is evenly mixed prior to administration. Each pack contains 4 single-dose pre-filled pens.

6.2 Source of IMP, Manufacture and Distribution

Exenatide (Bydureon or Bydureon BCise) will be sourced from routine hospital stock and their handling and management will be subject to standard procedures of the pharmacy.

6.3 Storage and handling of IMP(s) at site

All IMP aspects of the trial at participating sites are the responsibility of the PI, who may delegate this duty to the local pharmacist or other appropriately trained personnel. The delegation of duties must be recorded on the Staff Signature and Delegation of Tasks.

Storage and handling (e.g., labelling) of the IMP will be completed in accordance with the relevant SPC and summary of drug arrangements. Exenatide requires refrigerated storage (2-8°C). Once removed from the refrigerator, Exenatide needs to stand at room temperature for at least 15 minutes before administration. All patients will be instructed how to operate the pen device and to perform the injections. They will perform their first injection with supervision of the trial team at the end of the baseline visit.

For home visits, dispensing of IMP will be performed by trial pharmacy and transported to the patient in an appropriate cool bag with temperature logger by the clinical trial team. The trial team member will check the temperature logger to ensure the temperature has stayed within the range 2-8°C. If the temperature has fallen out of range the IMP must not be dispensed to the patient and should be returned to the trial pharmacy.

Detailed instructions are contained in the summary of drug arrangements.

6.4 Accountability of IMP(s)

The trial pharmacist within the hospital pharmacy will be accountable for trial drug supplies. There will be no additional reconstitution or other preparation required prior to dispensing from hospital stock.

The IMP Drug Accountability Log must be completed to record each dose of IMP dispensed for each trial participant. This log must be retained in the relevant section of the Pharmacy Site File, and a copy must be submitted to the sponsor upon request. It is the responsibility of the Pharmacy Lead to maintain drug accountability records.

The patient will be instructed to return unused IMP to the research facility, which will then be returned to site pharmacy, to be then updated in the drug accountability log in the pharmacy site file. Following authorisation by the sponsor, drug destruction will be conducted in accordance to local practice and this will be documented in the drug destruction log in the hospital pharmacy file.

Detailed instructions are contained in the summary of drug arrangements.

6.5 Concomitant medication

Trial participants will be permitted to use any licensed medication throughout the course of the trial that is recommended by their referring Neurologist and is not contraindicated with trial IMP as per standard practice. Patients will be given advice in any necessary minor adjustments to their pre-existing MSA medications at each of their follow up visits and doses will be recorded and converted to a Levodopa equivalent dose (LED) as appropriate. No routine adjustment of MSA medications will be made by the Investigator(s) unless at the request of the patients. If possible, patients will be invited to attend the trial site at a similar time of day and after a similar duration since they took their usual MSA medications for each of the trial visits.

Patients receiving warfarin or coumarin derivatives may be at risk of increased INR and associated bleeding; therefore INR should be monitored closely at each participant's visit.

Patients on Warfarin will not be able to undergo Lumbar punctures.

There have been rare reported events of altered renal function with Exenatide; therefore patients receiving the following concomitant medications should have their renal function closely monitored using blood tests at every follow up visit:

- angiotensin converting enzyme inhibitors,

- angiotensin-II antagonists,
- non-steroidal anti-inflammatory medicinal products
- diuretics

COVID-19 vaccinations that are administered after a patient has signed informed consent should be captured as a concomitant medication. If the vaccination is a multi-dose vaccination, each dose received should be entered as a separate concomitant medication.

Concomitant medications will be recorded in the participant's notes in the local electronic health record system, EPIC.

6.6 Post-trial IMP arrangements

The IMP will not be provided to trial participants' post-trial participation.

7 Selection of Participants

The investigator should only enrol subjects who meet all inclusion and none of the exclusion criteria, are not put at undue risk by participating in the trial and can be expected to comply with the protocol.

There will be NO EXCEPTIONS to eligibility requirements at the time of randomisation. Previous clinical correspondence will be used to confirm eligibility criteria. Questions about eligibility criteria should be addressed PRIOR to attempting to randomise the participant.

The eligibility criteria for this trial have been carefully considered and are the standards used to ensure that only medically appropriate participants are entered. Participants not meeting the criteria should not be entered into the trial for their safety and to ensure that the trial results can be appropriately used to make future treatment decisions for other people with similar diseases or conditions. It is therefore vital that exceptions are not made to these eligibility criteria.

Participants will be considered eligible for enrolment in this trial if they fulfil all the inclusion criteria and none of the exclusion criteria as defined below.

7.1 Eligibility of trial participants

7.2 Trial participant inclusion criteria

1. Male or female participants aged 30-80 years old with a diagnosis of Possible or Probable MSA of the parkinsonian subtype (MSA-P) or cerebellar subtype (MSA-C) according to The Gilman Criteria (Gilman et al. 2008)
2. Participants who are less than five years from the time of documented MSA diagnosis or from the time of documented parkinsonian / ataxic neurological condition that later turns out to be MSA.
3. Participants who are able to walk at least 10 metres with or without assistance.
4. Participants with an anticipated survival of at least three years in the opinion of the investigator.

5. Willing to adhere to the study drug regimen.
6. Willing and able to meet all study requirements, including travel to Study Centre, procedures, measurements and visits, including:
 - a. Caregiver/trial partner committed to facilitate participants involvement in the study if the participant is unable to attend appointments on their own.
7. Females of childbearing potential and males with partners of childbearing potential agree to use an effective method of double contraception from the time consent is signed until at least 12 weeks after treatment discontinuation.
8. For Females of childbearing potential; they must have had a negative pregnancy test within 7 days prior to being randomised. Participants are considered not of child bearing potential if they are surgically sterile (i.e. they have undergone a hysterectomy, bilateral tubal ligation, or bilateral oophorectomy) or they are postmenopausal
9. Willing and able to provide written informed consent. Subjects who are not able to write may give verbal consent in the presence of at least one witness, and the witness should sign the informed consent form.

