8.1 Pre-treatment Assessments

Screening assessments – Visit 1

Short title: Exenatide once-weekly as a treatment for Multiple System Atrophy Sponsor code: 125591

Participants will attend the research centre for informed consent to the trial. The following trial specific procedures will be carried out after consent to assess the participant's eligibility:

- Demographics recorded
- Medical History recorded
- Family History recorded
- All available brain imaging will be recorded
- Any previous genetic tests recorded e.g. if testing has been performed for Spinocerebellar ataxia or Fragile X tremor/ataxia syndrome
- Previous drug compliance issues recorded
- Physical Examination
- Neurological Examination
- 12-Lead ECG
- Routine bloods (FBC, U&E, LFT, glucose, amylase, HbA1c, PT and APTT)
- Height and weight
- Vital signs
- Serum and urine pregnancy test (for women of child bearing potential)
- MoCA
- BDI-II
- Concomitant Medications

At this visit the investigator will also ensure the patient is asked about speech/swallowing and mobility to assess exclusion criteria number 3. Eligible patients will wear a sensor attached by sticking plaster over their lower back for 1 week. They will bring this back to the trial team at the baseline visit or send to the trial team using a Stamped Addressed Envelope.

Participants will be randomised to either the trial drug or control arm.

Week 0 (Baseline assessments) – Visit 2

Patients will attend the research centre for the following trial procedures:

- Physical Examination (if deemed necessary by trial clinician for clinical purposes)
- Neurological Examination (if deemed necessary by trial clinician for clinical purposes)
- Lumbar puncture for CSF collection
- Serum collection
- Fasting blood tests (glucose, insulin, c-peptide and triglycerides)
- Vital signs
- UMSARS
- COMPASS Select
- MSA-QoL scale
- Timed Motor Tests
- The Unified Dystonia Rating scale
- MoCA
- BDI-II

- Concomitant Medications review
- Adverse Events review

Participants randomised to the trial drug arm will be dispensed the trial medication and receive teaching on its use.

All pre-treatment procedures will be carried out as specified in the schedule of assessments (appendix 1).

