11.3 Randomisation methods

A random sequence for study arm allocation will be computer generated by a randomisation service provider (SealedEnvelope.com). Sealed Envelope will provide a unique trial identification code for each recruited participant. Stratified randomisation will be performed with strata defined by MSA sub-type. Blocking will be used within strata to enable achievement of equal numbers in each group.

Strata 1 = MSA of parkinsonian sub-type (MSA-P)

Strata 2 = MSA of cerebellar sub-type (MSA-C)

At the baseline visit, the clinical investigator will enter the patient's initials, gender, date of birth, date of consent, criteria fulfilment and MSA sub-type strata into the SealedEnvelope.com secure website which will then allocate the appropriate trial identification code to the patient.

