Appendix 1 - Schedule of assessments

1. Medical History: including MSA history, family history, medication history, previous imaging, previous genetic tests and previous drug compliance issues.
2. Vital signs: blood pressure, respiratory rate, heart rate, temperature, oxygen saturation and weight.
3. Routine blood tests: FBC, U&E, LFT, glucose, amylase, HbA1c, PT and APTT (PT and APTT not done at weeks 24 and 36).
4. Fasting blood tests
 - Baseline visit: glucose, insulin, c-peptide, and triglycerides.
 - Week 24 visit: glucose, insulin, c-peptide.
 - Week 48 visit: glucose, insulin, c-peptide.
5. 5 IMP administration: Participants will be randomly allocated into 2 groups to receive either Exenatide (n[~]=25) or best medical treatment (n[~]=25). Only participants randomised to the Exenatide arm will receive the IMP.
 6. At Week 4 the study nurse will call the participants to provide support and optimise compliance.
 7. At Week 58 the study nurse will call the participants to perform an adverse event check.

8. Randomisation will occur once eligibility has been confirmed prior to Visit 2 to allow Pharmacy team time to prepare IMP for dispensing.
9. * Clinical and Neurological examinations will be performed with deemed relevant/necessary by trial clinician for clinical purposes.
10. Only a serum sample will be collected for research purposes at week 96.

Appendix 2

COVID19 mitigation plans

The objective of this Appendix is to set out a plan detailing the proposed continuation of the Exenatide-MSA trial if a restriction in trial Face to Face visits should occur as a result of a resurgence of COVID19 infections.

CONTINUATION OF IMP DISPENSING FOR EXISTING TRIAL RECRUITS

1. Patient consent required. Each patient will be contacted by the research team, at site. Consent to ship IMP to the patients home to be fully documented in source notes
2. Patient will be assessed via telephone by Chief Investigator (or appropriate delegated trial team member) to decipher whether suitable to dispense IMP. Specific questions to be asked in relation to abdominal pain/ weight/ AEs/ new con-meds etc.

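### Criterion 8 ties the pregnancy test to randomisation rather than to the first exenatide dose, and no test is listed at the visit where that dose is given

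*Protocol*

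**What the plan says.** Criterion 8 in Protocol 7.2 requires of women of childbearing potential that "they must have had a negative pregnancy test within 7 days prior to being randomised". The Summary gives the same rule. Neither text mentions the first dose. Section 7 applies eligibility at the same point: "There will be NO EXCEPTIONS to eligibility requirements at the time of randomisation".

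In Section 8.1, serum and urine pregnancy tests appear in the Visit 1 list only. The Visit 2 (baseline) list has no pregnancy test. Section 8.5 includes a urine pregnancy test among the local laboratory tests but names no visit. Appendix 1 and SAP Table 1 show an eligibility confirmation at baseline, with no test attached to it.

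On the first dose, Section 6.3 says of the patients: "They will perform their first injection with supervision of the trial team at the end of the baseline visit".

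On the time of randomisation the protocol gives two accounts. Appendix 1, footnote 8 says "Randomisation will occur once eligibility has been confirmed prior to Visit 2 to allow Pharmacy team time to prepare IMP for dispensing". In Section 11.3, "At the baseline visit, the clinical investigator will enter the" randomisation details into the web system, which puts it on the day of Visit 2.

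**The concern.** The 7-day limit protects the dose only if randomisation and dosing fall on the same day. Under footnote 8 they do not. A woman can then meet every criterion and receive her first injection more than 7 days after her only test, and nothing in the Visit 2 procedures would detect a pregnancy that began or became detectable in between.

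The consequence would be exposure of a pregnancy to the drug. Section 9.7 says there are no safety data on exenatide in pregnancy, and it counts exposure as running for at least 10 weeks after administration. Stopping the drug once a pregnancy is found therefore does not reverse the first dose. Pregnancy is already an exclusion (7.3, criterion 1), so the protocol intends that no pregnant woman be dosed. The schedule does not verify this at dosing.

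**Working it through.** The plan states no figure for the test-to-dose gap, so there is none to reproduce. The check is day arithmetic on the visit schedule.

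**Inputs**
- Test to randomisation: at most 7 days (7.2, criterion 8).
- Screening window: Day -28 to Day -1 (Appendix 1). A Visit 1 test is therefore at most 28 days before dosing.
- First dose: Day 0, at the end of Visit 2 (6.3; Section 8.3 also places it in clinic).
- Randomisation to first dose: d days. The protocol states no maximum.
- Sensor wear: one week before the baseline visit, starting at Visit 1 (8.1, 8.6). A Visit 1 test is therefore normally about 7 days old or more at Visit 2.

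**Formula**

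Criterion 8 allows the test on any day from Day -(d + 7) to Day -d, and the screening window cuts this off at Day -28. Hence the longest permitted gap is min(28, d + 7) days.

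| d (days) | Longest permitted gap (days) | Reading |
|---|---|---|
| 0 | 7 | Randomised at the baseline visit (11.3) |
| 1 | 1 + 7 = 8 | Footnote 8, short lead time |
| 5 | 5 + 7 = 12 | Footnote 8, short lead time |
| 7 | 7 + 7 = 14 | Footnote 8, one week earlier |
| 14 | 14 + 7 = 21 | Footnote 8, two weeks earlier |
| 21 or more | 28 | Visit 1 on Day -28, randomised by Day -21 |

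The range d = 1 to 5 is an assumption. Footnote 8 gives pharmacy lead time as its only reason, and Section 6.4 says "There will be no additional reconstitution or other preparation required prior to dispensing from hospital stock", so a long lead time is not expected. In that range, with the Visit 1 test as the only one, the actual gap is about 7 to 12 days: sensor wear sets the lower end and criterion 8 the upper. If Visit 1 is earlier than Day -(d + 7), criterion 8 itself forces a repeat test before randomisation.

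**Which account of randomisation is better supported**

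Section 8.1 agrees with footnote 8. It mentions randomisation at the end of the Visit 1 text, and under Visit 2 it refers to participants already allocated to the drug arm. Section 11.3 says otherwise. Section 8.2 can be read either way, because it lists the Section 8.1 assessments, which include Visit 2, ahead of randomisation.

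Under 11.3 the gap is capped at 7 days, but a Visit 1 test about 7 days old would only just meet criterion 8 or would fail it. No repeat test appears in the visit lists.

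**Weak evidence set aside**

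Appendix 1 as available shows no pregnancy-test row at all, even for Visit 1, where 8.1 requires one. A row may have been lost when the PDF was read. The conclusion rests on the Section 8.1 Visit 2 list, which is intact.

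**The case against.** The case against is that this asks for an extra precaution and corrects no fault. Testing within 7 days of randomisation is a stated, bounded rule, and no text sets a dosing-day standard that the protocol then misses. Under 11.3 there is no excess gap. Under footnote 8 with d of 1 to 5 days, the excess over the accepted 7 days is only 1 to 5 days. The 28-day case needs randomisation three weeks before dosing, which no text describes.

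The interval is also not unprotected. Double contraception runs from consent (criterion 7). Pregnant women, women planning pregnancy and women without acceptable contraception are excluded. Two kinds of test are done at Visit 1, eligibility is confirmed again at baseline, a urine test is available locally, and there is an adverse-event call at Week 4. The protocol relies on contraception throughout 48 weeks of dosing, so a few days before the first dose add little risk.

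Most of this stands, and it limits the size of the point. The gap depends on footnote 8, it is probably a matter of days, and few women are involved. It does not remove the point, because none of the listed safeguards is a test before the first dose. Footnote 8, which creates the gap, is also the account of randomisation that fits the order of Section 8.1.

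**Conclusion.** The concern holds, at low priority. If footnote 8 is followed, the plan permits a first dose more than 7 days after the only pregnancy test: up to 8 to 12 days if randomisation precedes dosing by 1 to 5 days (assumed), and 28 days at the extreme. If randomisation takes place at the baseline visit, the cap is 7 days and there is no excess.

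The documents do not say how many women of childbearing potential will enrol. Few are likely: ages run from 30 to 80, postmenopausal and surgically sterile women fall outside the definition, and only about 25 of the 50 participants receive the drug. There is no breach of criterion 8 and no effect on the sample size or primary analysis. The case for acting is a possible exposure that cannot be undone, set against a very small cost.

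**What to change.** - Add a urine pregnancy test to the Visit 2 procedures in Section 8.1 for women of childbearing potential in the exenatide arm, with a negative result required before the first injection. The test-to-dose gap is then 0 days under either account of randomisation.
- Add a pregnancy-test row to Appendix 1, marked at Visits 1 and 2.
- As a minor alignment, make Section 11.3 agree with footnote 8 on when randomisation occurs. If randomisation is kept at the baseline visit instead, do the Visit 2 test before randomising so that it also satisfies criterion 8.

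Criterion 8 itself needs no change.

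The cost is one urine test, already in the Section 8.5 list, for a few participants at a visit that already collects samples, plus one line, one table row and one sentence of text. The one drawback is that a rare positive would be found after randomisation. Under SAP 5.3 that participant would stay in the intention-to-treat population undosed.
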